4.4. Exclusion Criteria

- 1 Subjects who, in the twelve months prior to their enrolment assessment had undergone:
 - a. cosmetic facial plastic surgery (other than rhinoplasty),
 - b. tissue grafting (e.g., fat injections),
 - c. tissue lifting implants (e.g., threads, barbs) or other implants,
 - d. augmentation with any permanent or semi-permanent filler (e.g., silicone, PMMA, PLLA) or temporary filler (e.g., Ha, CaHA, PCL)
 - e. neuromodulator injections,
 - f. mesotherapy,
 - g. resurfacing in the mid-face (e.g., laser, radio frequency, dermabrasion, or chemical peel)

in the region of the face to be treated.

2 Subjects who have received any other facial aesthetic procedures (as described at exclusion criteria 1) at any time during the study period (see Table 2).

Table 2: MaiLi Volume and Extreme - Non-allowable treatments

Subject treatment area	No further aesthetic treatments are allowed in the region of:	Reason		
Mid-face	Nasolabial folds Nose	Adjacent to treatment area Effect on facial appearance is too significant		
	Tear troughs Prejowl sulcus Nasojugal folds	Area assessed within mid-face scale Area assessed within mid-face scale Area assessed within mid-face scale		
Jawline/Jowls	Nose Pre-jowl sulcus Marionette lines	Effect on facial appearance is too significant Adjacent to treatment area Adjacent to treatment area		
Chin	Nose Platysma Pre-jowl sulcus Lips	Effect on facial appearance is too significant Adjacent to treatment area Adjacent to treatment area Lips are reference points for chin scoring scale		
Temples	Nose Periorbital lines Forehead	Effect on facial appearance is too significant Adjacent to the treatment area Adjacent to the treatment area		

- 3 Subjects currently enrolled in other clinical trials.
- 4 Subjects with facial hair as this could interfere with study evaluations.
- 5 Subject who had been deprived of their freedom by administrative or legal decision or who is under guardianship.
- 6 Subject is an employee of the aesthetic surgery department of the investigational site, the CRO or study sponsor.
- 7 Pregnant or nursing woman or planning a pregnancy during the study.
- 8 Subjects taking thrombolytics or anticoagulants.
- 9 Subjects with bleeding disorders.
- 10 Subjects with known hypersensitivities to hyaluronic acid, lidocaine. amide local anaesthetics or other components of the treatment.
- 11 Subjects with a history of severe allergy or anaphylactic shock.

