- 12 Subjects with active (or a history of) autoimmune disease.
- 13 Subjects with porphyria.
- 14 Subjects with cutaneous disorders and areas affected by inflammation and/or infectious skin problems (e.g., acne, herpes) at or near the treatment site
- 15 Subjects with a tendency to form keloids, hypertrophic scars or any other healing disorders
- 16 Subjects with known history of precancerous lesions/skin malignancies.
- 17 Subjects must avoid receiving COVID-19 vaccination for the 14 days before and following injection.

STUDY DESIGN AND PROCEDURES/METHODOLOGY

The study is a 24-month, open-label, prospective, post-market clinical follow-up trial, conducted in compliance with ISO 14155:2020, the International Conference on Harmonization (ICH), and Good Clinical Practice (GCP) principles. The trial will be approved by the ethical committee of the participating sites and complied with local regulatory authority requirements. Following the guidelines of the European Standard for Aesthetic medicine services-non-surgical medical treatments, which lists the allowed aesthetic procedures, premises, and training requirements to conduct aesthetic procedures for doctors.

Potential subjects who visit the clinic for aesthetic procedures will be explained about the study by the investigators for recruitment and informed consent will be taken from the subjects before the study procedures.

Potential subjects will first be registered at the clinic. The investigator will explain the study to the subjects, including details of the treatment procedure and the associated benefits and risks. The subjects will be given time to read the consent form and clarify any questions they have about the study with the investigator. The subject should be informed of the product's indications, contraindications, precautions, warnings, expected results, and potential adverse events and questioned on her/his medical history. In addition, the subject must be given the option to indicate whether he/she would like to remain unidentifiable in the photographs (through the use of a black box) and whether the photographs may be used for publication and promotion of the medical devices.

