The content of the syringe is sterile until opening. The external surface of the syringe is not sterile and should not be used in a controlled environment such as an operation room. If needed, the surface of the syringe must be cleaned up in respect of the aseptic techniques in place.

Once the treatment is done, a safety assessment will be conducted and the investigator will do another photographic assessment of the subject. The investigator will complete the electronic case report form (eCRF) of the subject before giving instructions for the next follow-up appointment. The subject will be given a diary card to bring home and record any adverse reactions they experience. The subject will then bring back the diary card on their first follow-up appointment 2 weeks after the treatment. The diary card will be reviewed and documented down by the investigator.

For the subsequent follow-up visits (i.e. 3 months, 6 months, 12 months, 18 months, and 24 months after the treatment), the subject will be given a questionnaire to assess their overall satisfaction with the results of their treatment (see appendix 5).

During the study, two independent evaluators will be involved:

• An on site live independent evaluator (I) (one for each site (4)) will be responsible for

- conducting the live Global Aesthetic Improvement Scale (GAIS) assessment during the subject's scheduled visits at 3, 6, 12, 18, and 24 months (see appendix 7). This assessment will be done in comparison to the face of the subject (at the time of the visit) and the 'full face' photograph taken at the baseline visit.
- A blinded independent evaluator (II) (one per country (2)) will be responsible for the remote assessment of the photographs using the different aesthetic grading scales (namely: Allergan Mid-Face Volume Deficit Scale, Merz Aesthetics scale for Jawline, Allergan Chin Retrusion Scale, and/or Allergan Temple Hollowing Scale). This evaluator will do the assessment of the photographs of all performed visits at month 6 (to generate the data for the interim 6 months report) and 24 (for the final report) of the follow-up period.

Photographs will be taken at each visit, and assessed by a blinded independent evaluator at 6 months and 24 months.

All data collected for the study will be kept in a secure place and is only accessible to the study's team members.

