- Do not re-use (risk of contamination). The product is intended for single use only.

- Do not use a syringe for several subjects (risk of cross-contamination).
- Do not used simultaneously with chemical peels, dermabrasion, laser treatment or radiofrequency treatment.
- Treatment with MaiLi Volume or MaiLi Extreme in combination with drugs and other devices has not been clinically evaluated.
- The investigator should exercise special caution when treating areas in close proximity to vulnerable structures such as vessels and nerves.
- Warn the subject to avoid exposure to the sun, UV rays, and temperatures below 0 °C, sauna, or hammam sessions during the two weeks following the injection procedure.
- Warn the subject not to use cosmetic products (e.g. makeup, skincare products) during the twelve hours following the injection treatment.
- Warn the subject to avoid applying intense pressure or massaging the treatment site for a few days following the injection.
- Warn the subject who are on medication that affects platelet functions (aspirin or non-inflammatory drugs) of the potential increased risks of haematomas and bleeding during the injection.
- The investigator should consider that the product contains lidocaine, at a concentration identical to that in the majority of HA products containing lidocaine. For normal healthy adults, the maximum total dose of lidocaine should not exceed 200 mg per session. When using concurrently (case of topical administration), the total administered dose of lidocaine should be considered. The concomitant use of other local anaesthetic agents should also be considered since the systemic toxic effects may be additive. Care should be taken for subjects with congenital methaemoglobinemia and subjects who are receiving concomitant treatment with methaemoglobin-inducing agents. In the case of athletes, the presence of lidocaine may produce a positive result in anti-doping tests.

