8. SAMPLE SIZE AND STATISTICAL METHODS

8.1. Determination of Sample Size

The study population will include all subjects who are enrolled, and the entire study population will be included in statistical analysis.

Average Efficacy=85% Lower bound of 95% Confidence Interval (CI) =65% Clinical Margin=-20% Alpha=5% Power= 80% (Beta =0.20)

Considering 20% dropout rate, a total of 168 subjects (42 per site; a minimum of 36 per site respectively), to meet a completed study size requirement of 140, will be recruited.

- Mild to significant facial volume deficit (mid-face area) (n=60 (50), MaiLi Volume 30 (25) subjects and MaiLi Extreme 30 (25) subjects)
- Mild to moderate jawline ptosis (n=36 (30), MaiLi Extreme)
- Minimal to severe chin retrusion (n=36 (30), MaiLi Extreme)
- Minimal to severe temporal hollowing (n=36 (30), MaiLi Volume)

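### Exclusion 1(g) limits the 12-month resurfacing look-back to the mid-face, in conflict with the list's own treated-region rule, so read literally it excludes no one treated only at the jawline, chin or temple

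*Protocol*

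**What the plan says.** Exclusion criterion 1 (section 4.4, repeated in the synopsis) opens with "Subjects who, in the twelve months prior to their enrolment assessment had undergone" and lists seven kinds of procedure, a to g. Items a to f name no facial region. They take theirs from the words that close the list: "in the region of the face to be treated". Item g names its own region: "g. resurfacing in the mid-face (e.g., laser, radio frequency, dermabrasion, or chemical peel".

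Three other provisions come near the subject:
- Criterion 2 of section 4.4 excludes "Subjects who have received any other facial aesthetic procedures (as described at exclusion criteria 1) at any time during the study period (see Table 2".
- Criterion 14 excludes "Subjects with cutaneous disorders and areas affected by inflammation and/or infectious skin problems (e.g., acne, herpes) at or near the treatment site".
- The contraindications and warnings in the study design section say "Do not used simultaneously with chemical peels, dermabrasion, laser treatment or radiofrequency treatment".

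The study treats four areas. Section 8.1 plans three groups outside the mid-face (jawline, chin and temple), each of the size given for the first: "Mild to moderate jawline ptosis (n=36 (30), MaiLi Extreme". The primary endpoint (section 2.1) is the proportion with a GAIS score of 3 or above at 6 months. Of the GAIS rating, the study design section says: "This assessment will be done in comparison to the face of the subject (at the time of the visit) and the 'full face' photograph taken". The picture meant is the baseline one.

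**The concern.** The protocol itself treats resurfacing within 12 months as a reason to keep a subject out when the mid-face is the area treated. It gives no reason for not applying the same rule to the other three areas. As written, a subject could have laser, radiofrequency, dermabrasion or a peel on the jawline, chin or temple shortly before enrolment and still enter for treatment of that area.

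This matters because the study is open-label and has no untreated control, so change from any source after baseline cannot be separated from change due to the filler. GAIS is a rating of appearance, and its grade 3 (Table 3) requires only improvement on the initial condition. Section 4.2 recruits people who come to the clinic for aesthetic procedures, so recent resurfacing is a plausible history. Its frequency is not given.

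**Working it through.** **Step 1: which prior resurfacing excludes a jawline-only subject?** Chin and temple give the same answers.

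| Reading of item g | Resurfaced on the jawline | Resurfaced in the mid-face |
|---|---|---|
| Both limits apply (literal) | eligible | eligible |
| Only the mid-face limit applies | eligible | excluded |
| Only the closing line applies | excluded | eligible |

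Item g protects the treated area outside the mid-face only if its own words are disregarded. Sites could apply it differently.

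**Step 2: does anything else close the gap before baseline?**
- Criterion 2 and Table 2 concern procedures during the study, not before it. Criterion 2 in section 4.4 also refers back to criterion 1 for what counts as a procedure, so it inherits the unclear item.
- Criterion 14 needs diseased, inflamed or infected skin. Healed but recently resurfaced skin does not meet it.
- The device warning concerns simultaneous use and sets no interval.
- Prior treatments are recorded at baseline (Table 8, section 5.1.1), but recording does not exclude.

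**Step 3: planned subjects in the groups not reached** (section 8.1, by lead area).
- Recruited: 36 + 36 + 36 = 108; 108/168 = 64.3%.
- Completing: 30 + 30 + 30 = 90; 90/140 = 64.3%.

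Section 4.1 allows treatment of several areas, so the count is approximate. A temple-lead subject also treated in the mid-face is reached for the mid-face. A mid-face-lead subject also treated in the temples is not covered there.

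**Step 4: illustration of possible bias.** The protocol states no figure to reproduce here. Assume that a share f = 5% to 20% of a 30-completer group was recently resurfaced, and that in a fraction c = 25% to 100% of those who could change category the score is reversed. The product f × c then runs from 0.05 × 0.25 = 0.0125 to 0.20 × 1 = 0.20. All of these values are assumptions.

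- *Continuing improvement*, true rate p: apparent rate = p + (1 − p) × f × c.
 - p = 65% (the lower bound in section 8.1): 0.65 + 0.35 × 0.0125 = 65.4%, up to 0.65 + 0.35 × 0.20 = 72.0%. That is 0.1 to 2.1 extra responders in 30.
 - p = 85% (the expected efficacy in section 8.1): 0.85 + 0.15 × 0.0125 = 85.2%, up to 0.85 + 0.15 × 0.20 = 88.0%.
- *Fading effect*: apparent rate = p − p × f × c.
 - p = 85%: 0.85 − 0.85 × 0.0125 = 83.9%, down to 0.85 − 0.85 × 0.20 = 68.0%.

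In the exact binomial with n = 30 and p = 65%, 25 responders is the smallest count with an upper tail of at most 2.5%. The protocol does not state this success rule; it is used only to give scale. The chance of 25 or more is 2.3% at a rate of 65%, and rises to between 2.6% and 11.6% over the upward range.

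**The case against.** The strongest reply is that this is a drafting slip with little demonstrated effect. The closing words show the intent for the whole list. The mid-face phrase looks left over from a single-area text: the pre-injection check in the study design section likewise names only the mid-face. That is probably right, but it supports the correction, because sites apply the words on the page.

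The reply has more force against stronger readings that a reader might infer:

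- *That the effect of earlier resurfacing is credited to the filler.* Change already present at baseline is in the reference photograph and is not counted. Only later change could be misattributed, and it could go either way.
- *That resurfacing moves the severity scales by a grade.* The chin scale grades the position of the chin midpoint, the temple scale concavity, and the jawline scale contour and volume (Tables 5 to 7). Table 11 describes GAIS as measuring volume restoration and recontouring. Nothing in the protocol shows that resurfacing shifts any of these. Some influence on a global appearance rating cannot be ruled out, but no more than that can be said.
- *That 108 subjects are affected, or that each moves the rate by 3.3 points.* The 108 are those in groups that item g does not reach. The 3.3 points (1/30) are a ceiling, for a subject certain to fail who is certain to be converted. Weighted by the chance of failing, the largest expected upward shift per resurfaced subject is 0.15/30 = 0.5 points at 85%, or 0.35/30 = 1.2 points at 65%.
- *That results cannot be compared across areas.* No such comparison is among the objectives.
- *That the adverse event count is distorted.* Criterion 14 keeps out inflamed skin, and section 6.2.1 requires confounding factors to be considered in assessing causality. Little of this concern remains.

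**Conclusion.** The conflict is real and appears in both section 4.4 and the synopsis. On the literal reading, the 12-month resurfacing look-back excludes no one treated only at the jawline, chin or temple. Those lead-area groups make up 108 of 168 planned subjects (64%), and no other entry criterion covers prior resurfacing in those areas.

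The consequence is a possibility of bias in an uncontrolled appearance rating, in either direction and of unknown size. The ranges in the working rest on assumed prevalence and misclassification and show scale only. They are not estimates for this trial. The point deserves correction because it changes who may enter and is cheap to put right. It does not show that the primary result is biased.

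**What to change.** Reconcile item g with the closing words in section 4.4 and the synopsis, so that the resurfacing look-back applies by treated region, as items a to f do. Deleting the mid-face restriction from item g is one way.

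For subjects already enrolled, use the prior-treatment data recorded at baseline to flag those resurfaced in a treated region in the previous 12 months, and show the 6-month GAIS result for each area with and without them. This assumes that the record gives the date and region of the procedure; if it does not, sites would need to be queried. The analysis can sit in the statistical analysis plan.

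The cost is a short amendment in two places, a few more screen failures and one sensitivity analysis.

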4	Much improved	Marked improvement in appearance but not completely optimal		
5	Very much improved	Excellent corrective results		

Table 4: Assessment Scale for Mid-face volume deficit (see appendix 1²¹)

Grade	Severity	Definition				
0	None	 Moon face; Fullness (convexity) in the zygomaticomalar region, anteromedial cheek, and/or submalar region 				
1	Minimal	Flattening in the zygomaticomalar region, anteromedial cheek, and/or submalar region				
2	Mild	 Mild concavity in the zygomaticomalar region, anteromedial cheek, and/or submalar region; Mild tear troughs and/or nasolabial folds 				
3	Moderate	 Moderate concavity in the zygomaticomalar region, anteromedial cheek, and/or submalar region; Moderate tear troughs and/or nasolabial folds; Mild nasojugal folds and/or pre-jowl sulcus; Mild prominence of bony landmarks; Mild visibility of musculature 				
4	Significant	 Significant concavity in the zygomaticomalar region, anteromedial cheek, and/or submalar region; Significant tear troughs and/or nasolabial folds; Moderate nasojugal folds and/or prejowl sulcus; Moderate prominence of bony landmarks; Moderate visibility of musculature 				
5	Severe	Wasting;Severe concavity in the zygomaticomalar region,				

	anteromedial cheek, and/or submalar region;
	 Severe tear troughs and/or nasolabial folds;
	 Significant nasojugal folds and/or prejowl sulcus;
	 Significant prominence of bony landmarks;
	Significant visibility of underlying musculature

Table 5: Assessment Scale for ptosis of Jawline (see appendix 2²²)

Grade	Severity	Definition		
0	None	Continuous jawline contour, no loss of jawline volume		
1	Mild	Mild loss of jawline contour and continuity, mild loss of volume in post-jowl region, loss of volume in pre-jowl region may be present.		
2	Moderate	Moderate loss of jawline contour and continuity, moderate loss of volume in post-jowl region, loss of volume in pre-jowl may be present.		
3	Severe	Severe loss of jawline contour and continuity, severe loss of volume in post-jowl region, loss of volume in pre-jowl region may be present		
4	Extreme	Extreme disruption of jawline contour, extreme post-jowl and pre-jowl volume loss		

Table 6: Assessment Scale for Chin retrusion (see appendix 3²³)

Grade	Severity	Definition		
0	None	No chin retrusion; chin midpoint at or in front of the lower vermilion border vertical line		
1	Minimal	Minimal chin retrusion; chin midpoint is between the labiomental sulcus vertical line and lower vermilion border vertical line		
2	Moderate	Moderate chin retrusion; chin midpoint is at labiomental sulcus vertical line		
3	Severe	Severe chin retrusion; chin midpoint slightly behind labiomental sulcus vertical line		
4	Extreme	Extreme chin retrusion; chin midpoint significantly behind labiomental sulcus vertical line		

Table 7: Assessment Scale for Temporal hollowing (see appendix 4²⁴)

Grade	Severity	Definition	
0	Convex	Rounded temple	
1	Flat	Flat temple; temporal fusion line may be visible	
2	Minimal	Shallow depression or concavity with minimal volume	
		loss; temporal fusion line may be visible	
3	Moderate	Moderate depression or concavity with moderate volume	
		loss; moderate prominence of the temporal fusion line	

4	Severe	Deeply	recessed,	sunken	appearance,	marked
		prominence of temporal fusion line and zygomatic arch				atic arch

Subjects and investigator will also be given a questionnaire (see appendix 5) to assess the appearance of their mid-face volume deficit, jawline ptosis, chin retrusion, or temple hollowing before the treatment.

The investigator will then proceed to thoroughly disinfect the treatment area with an appropriate antiseptic solution (e.g. chlorhexidine digluconate (CHX) solution). The investigator will ensure:

- The correct product (MaiLi Volume or MaiLi Extreme);
- The correct subject (double identifiers i.e. full name, date of birth and/or medical identification (ID) number) and
- Correct indication (into the subcutaneous layer and supraperiostic zone of the mid-face) before the procedure.

The investigator will assemble the MaiLi Volume or MaiLi Extreme syringe and the appropriate needle (27G $\frac{1}{2}$). Depending on the treatment site, the depth of injection, and gel quantity to be injected, the investigator will decide the injection technique to be used for the treatment. The investigator will begin to slowly inject MaiLi Volume or MaiLi Extreme on the subcutaneous fat tissue or into the supraperiosteal zone of the subject's facial treatment area. It is recommended to use the technique of linear threading injection, multipoint injection, or a combination of both techniques. Then, the treated area will be massaged by the investigator to ensure the uniform distribution of the gel.

Investigator will be given a questionnaire (see appendix 6) to assess their satisfaction of using the MaiLi Volume or Extreme product during the treatment procedure.

The content of the syringe is sterile until opening. The external surface of the syringe is not sterile and should not be used in a controlled environment such as an operation room. If needed, the surface of the syringe must be cleaned up in respect of the aseptic techniques in place.

Once the treatment is done, a safety assessment will be conducted and the investigator will do another photographic assessment of the subject. The investigator will complete the electronic case report form (eCRF) of the subject before giving instructions for the next follow-up appointment. The subject will be given a diary card to bring home and record any adverse reactions they experience. The subject will then bring back the diary card on their first follow-up appointment 2 weeks after the treatment. The diary card will be reviewed and documented down by the investigator.

For the subsequent follow-up visits (i.e. 3 months, 6 months, 12 months, 18 months, and 24 months after the treatment), the subject will be given a questionnaire to assess their overall satisfaction with the results of their treatment (see appendix 5).

During the study, two independent evaluators will be involved:

• An on site live independent evaluator (I) (one for each site (4)) will be responsible for

- conducting the live Global Aesthetic Improvement Scale (GAIS) assessment during the subject's scheduled visits at 3, 6, 12, 18, and 24 months (see appendix 7). This assessment will be done in comparison to the face of the subject (at the time of the visit) and the 'full face' photograph taken at the baseline visit.
- A blinded independent evaluator (II) (one per country (2)) will be responsible for the remote assessment of the photographs using the different aesthetic grading scales (namely: Allergan Mid-Face Volume Deficit Scale, Merz Aesthetics scale for Jawline, Allergan Chin Retrusion Scale, and/or Allergan Temple Hollowing Scale). This evaluator will do the assessment of the photographs of all performed visits at month 6 (to generate the data for the interim 6 months report) and 24 (for the final report) of the follow-up period.

Photographs will be taken at each visit, and assessed by a blinded independent evaluator at 6 months and 24 months.

All data collected for the study will be kept in a secure place and is only accessible to the study's team members.

MaiLi Volume or MaiLi Extreme may be administered only by an authorized physician in accordance with local legislation. These devices are designed to be injected into the subcutaneous fat tissue or the supraperiostic zone by a physician who has been specifically trained in injection techniques for dermal filler procedures. The physician's technical competence is crucial to the success of the treatment. All injections carry a risk of infection, aseptic techniques and standard practices should be employed to avoid contamination and infection. Deep knowledge of the anatomy of the area to be treated is essential and shall be used to perform similar interventions (i.e. cross-linked hyaluronic acid injection in the face area) in order to avoid perforation or compression of vessels, nerves, and other more fragile structures. Use of the supplied needle is recommended. The design, diameter, and length have been validated for optimum use with the injection. The usage of another needle could not ensure the correct fitting to the syringe and/or the correct delivery of the product

If the subject has an herpes zoster episode in the treatment area at the time of study visit, the subject can miss the visit (or attend for a safety assessment without an efficacy assessment/photographs) and attend the next study visit when the herpes has resolved.

In some cases of (serious) adverse events ((S)AE) related to the study product in one or more treatment areas, hyaluronidase might need to be injected into the treated facial area(s) to degrade the study product and contribute to manage the adverse event. Hyaluronidase has to be available on site. After, The (S)AE must be reported in accordance with the (S)AE guidelines. Hyaluronidase must be immediately available at each study site for rapid use if needed. The study investigator must be familiar with the guidelines for the appropriate use of hyaluronidase effectively for the effective management of the adverse event if required. A guidance document on the use of hyaluronidase in aesthetic practice is provided in appendix 8. After, The (S)AE must be reported in accordance with the (S)AE guidelines.

In case the subject is unsatisfied with the treatment, he/she will fill in a complaint form. This filled form will be sent to the Vigilance team for further assessment (for further information, see section 6.2.4.3.)

CONTRAINDICATIONS/WARNINGS:

- Do not inject subjects having known risk of hypersensitivity to hyaluronic acid or lidocaine or amide local anaesthetics.
- Do not inject subject having history of severe allergy or anaphylactic shock.
- Do not inject subjects suffering from autoimmune disease.
- Do not inject subjects suffering from porphyria.
- Do not inject subjects having cutaneous disorders, inflammation or infection (herpes, acne, etc.) at the treatment site or nearby.
- Do not inject subjects for whom the medical history shows a sensitivity that could lead to a reaction to the treatment.
- Do not use in subjects with bleeding disorders or in subjects who are undergoing treatment with thrombolytics or anticoagulants.
- Do not inject subjects with a tendency to form keloids, hypertrophic scars or any other healing disorders.
- Warn subjects who have a medical history of herpes zoster of the potential risk of reactivation before deciding to participate in the study.
- Do not use during pregnancy or breast-feeding.
- Do not use for children.
- Do not inject into blood vessels (intra-vascular) or directly near blood vessels (for avoiding vessels compression). An unintended intravascular administration can cause high blood concentration and acute central nervous system and cardiovascular toxic symptoms.
- Do not inject in area other than the face (e.g. hands, body).
- Do not inject MaiLi Volume/Extreme in the periorbital area (eyelids, palpebromalar groove, crow's feet) and glabellar region.
- The injection of MaiLi Volume/Extreme into the subcutaneous fat tissue or into the supraperiostic zone is reserved to specialists specifically trained in these injection techniques.
- Do not inject intramuscularly. There is no available clinical data about injection of MaiLi Volume/Extreme into an area which has already been treated with another brand of resorbing product. It is therefore recommended not to inject in areas in which another brand of resorbing
- product is not still fully resorbed.
- Do not inject jointly with another brand of resorbing product in the same area.
- Do not inject jointly with a permanent product.
- Do not mix with other products.
- Do not re-sterilise the product (the syringe and/or the needle).
- Do not inject more than 20 mL per year per subject.
- Do not inject more than 2 mL per treatment area during each session.
- Do not overcorrect.
- Do not use after expiry date or if the packaging is damaged or the syringe opened.
- Do not re-use (risk of contamination). The product is intended for single use only.

- Do not use a syringe for several subjects (risk of cross-contamination).
- Do not used simultaneously with chemical peels, dermabrasion, laser treatment or radiofrequency treatment.
- Treatment with MaiLi Volume or MaiLi Extreme in combination with drugs and other devices has not been clinically evaluated.
- The investigator should exercise special caution when treating areas in close proximity to vulnerable structures such as vessels and nerves.
- Warn the subject to avoid exposure to the sun, UV rays, and temperatures below 0 °C, sauna, or hammam sessions during the two weeks following the injection procedure.
- Warn the subject not to use cosmetic products (e.g. makeup, skincare products) during the twelve hours following the injection treatment.
- Warn the subject to avoid applying intense pressure or massaging the treatment site for a few days following the injection.
- Warn the subject who are on medication that affects platelet functions (aspirin or non-inflammatory drugs) of the potential increased risks of haematomas and bleeding during the injection.
- The investigator should consider that the product contains lidocaine, at a concentration identical to that in the majority of HA products containing lidocaine. For normal healthy adults, the maximum total dose of lidocaine should not exceed 200 mg per session. When using concurrently (case of topical administration), the total administered dose of lidocaine should be considered. The concomitant use of other local anaesthetic agents should also be considered since the systemic toxic effects may be additive. Care should be taken for subjects with congenital methaemoglobinemia and subjects who are receiving concomitant treatment with methaemoglobin-inducing agents. In the case of athletes, the presence of lidocaine may produce a positive result in anti-doping tests.

